## I. PURPOSE OF THE STUDY AND BACKGROUND

### A. Purpose of the Study

The proposed study “Integrated Community-Clinical Linkage Model to Promote Weight Loss among South Asians with Pre-Diabetes” aims to test the effectiveness and assess the implementation process of an integrated intervention to support weight loss for South Asian patients at-risk for type-2 diabetes mellitus (T2DM) in primary care settings. The primary outcome is  $\geq 5\%$  weight loss among South Asian patients at-risk for T2DM. The integrated intervention involves:

1. An electronic health record (EHR) intervention for primary care providers (PCPs) utilizing embedded alerts to increase screening and identification of South Asian patients at-risk for T2DM with  $BMI > 23 \text{ kg/m}^2$  and registries to track outcomes: and
2. Registry-driven community health worker (CHW)-led health coaching for patients. Using a stepped-wedge design, we will implement the study in 20 NYC PCPs enrolling 1040 South Asian patients at-risk for T2DM.

In addition, using a mixed-methods approach and the RE-AIM evaluation framework, we aim to systematically assess the implementation process and delineate factors that influence adoption, sustainability, and scalability of the integrated EHR-CHW intervention within applied practice settings. This will be achieved through the completion of:

3. Provider Surveys (n=80) to capture data on satisfaction with workflow before and after intervention, information sources for EHR-CHW initiatives before and after intervention, acceptability of and satisfaction with the integrated EHR-CHW intervention, and barriers and facilitators of point-of-care use of the tools.
4. Key Informant Interviews (n=100) with physician champions at each site and/or administrator of each site, Healthfirst representatives, community advisory board members, research staff, and CHWs. At baseline, the interviews will be incorporated into the workflow analysis to assess current satisfaction and usage of EHR and health coaching. At follow-up, the interviews will assess barriers and facilitators to the implementation and adoption process of the integrated EHR-CHW intervention, fidelity to the interventions, and to solicit recommendations for the replication and scalability of the intervention to other sites and insurer organizations.

**Impact:** The proposed study will inform efforts to prevent diabetes and promote weight loss in a high-risk population and generate a reproducible, scalable, and sustainable model for use with other insurer groups and clinical settings that work in immigrant populations with a high burden of chronic disease. The contributions of this study to generalizable knowledge are further described in the “Background”.

### B. Background

**B1. South Asians in the U.S. and NYC are a rapidly growing population.** Asian Americans currently comprise 5% of the U.S. population and make up approximately 40% of the immigrants entering the country. By 2050, the number of Asian Americans nationally is projected to grow to over 43 million. In this proposal, we focus on the *South Asian community*, who are among the largest and fastest growing Asian subgroups in the U.S. and NYC. South Asian Americans are comprised of individuals from India, Bangladesh, Pakistan, Sri Lanka, Nepal, and Bhutan. The NYC South Asian community grew by 49% during the years 2000 to 2010, from 216,179 to 323,675. (Asian American Federation, 2013a, 2013b, 2013c) Though there is substantial diversity in the socio-economic profile of South Asians across various subgroups, a significant portion of South Asians live in poverty (ranging from 17% of Asian Indians to 32% of Bangladeshis), have limited English proficiency (ranging from 25% of Asian Indians to 53% of Bangladeshis), and have access to fewer culturally appropriate community resources. For the purposes of our study, South Asians will be defined as individuals who self-identify

as South Asian, including those from India, Bangladesh, Pakistan, Sri Lanka, Nepal, and Bhutan, Guyana, Trinidad.

**B2. Diabetes & Pre-Diabetes is significantly higher among South Asians compared with Non-Hispanic Whites.**

Among Asian Indians in the U.S., cardiovascular disease (CVD) is the leading cause of death, and mortality due to T2DM has been increasing over time. Rates of T2DM and pre-diabetes in the U.S. South Asian community are high, with national data revealing the highest prevalence of diagnosed diabetes among Asian Indians compared to other Asian groups and compared to Non-Hispanic whites. In NYC, both population-based self-report and clinically measured rates of T2DM are high among South Asians. Rajpathak and colleagues report that foreign-born South Asians have a significantly higher prevalence of T2DM (35.4% vs 10.8%) compared to Whites, and had five times the odds of having T2DM compared to whites after adjustment for demographics and other potential confounders (AOR: 4.88, 95% CI (1.52, 15.66)). Similarly Gupta et al found that prevalence of self-reported diabetes diagnosis among South Asians of normal weight (using adjusted-BMI guidelines for Asians) in NYC were more than triple the rates of diabetes among Whites of normal weight (10.2% vs 2.9%, respectively). Estimates of clinically measured pre-diabetes in population-based studies and large community-based cohorts of South Asians in the U.S. have ranged between 16% to high as 33%. Thus, *scalable and translatable interventions that promote the early identification and prevention of diabetes in this population have significant potential for public health impact.*

**B3. South Asians develop diabetes at a lower BMI compared to other group.** South Asians report some of the highest BMI levels compared to other Asian groups and other minority/ethnic groups, ranging from 27% to 89% higher than the national average. A recent analysis of National Health & Nutrition Examination Survey (NHANES) data revealed that the average BMI for all Asian Americans surveyed was  $\leq 25$  kg/m^2, and yet they had the highest proportion of undiagnosed T2DM among all ethnic and racial subgroups surveyed. Due to these differences, in 2014 the American Diabetes Association (ADA) recommended lowering BMI cutoff points to  $\geq 23$  kg/m^2 for testing for T2DM in Asian American adults, including South Asians. Lowering BMI cutoff points as advised by the ADA could result in earlier identification of pre-diabetes and T2DM in Asian Americans, leading to improved primary and secondary prevention in these communities. *However, ADA recommendations have not been formally adopted in clinical settings for T2DM screening purposes despite compelling evidence for Asian American populations.*

**B4. Diabetes Prevention Program (DPP) is effective in in reducing incident diabetes in South Asians by achieving modest weight loss through behavior change.** Results from the U.S. Diabetes Prevention Program (DPP) indicated that modest weight loss through dietary changes and increased physical activity significantly reduced the incidence of T2DM in study participants. The Indian Diabetes Prevention Programme, modeled after the U.S. DPP, found that study participants who had modest weight loss ( $\leq 5\%$ ) were more likely to achieve normal fasting glucose at 6 and 24-month follow-up, which was associated with a 75% lower risk of developing incident T2DM after 2 years. Similarly, weight loss interventions conducted among South Asian immigrants in the United Kingdom and US have reported lower rates of developing incident T2DM and lower rates of insulin resistance. Though there have been few adaptations of DPP for the South Asian community, existing studies have demonstrated DPP's efficacy in increasing weight loss, diabetes knowledge, and positive behavioral changes such as healthful eating and/or engaging in physical activity. Our own work has tested the efficacy, feasibility, and acceptability of a cultural adaption of DPP for Bangladeshis and Asian Indians, demonstrating significant weight loss and behavior change among study participants.

**B5. DPP adaptations have utilized Community Health Workers (CHWs) for program delivery.**

Numerous studies have adapted and translated the DPP to different settings and contexts, with specific efforts to tailor program delivery for varied racial and ethnic groups. Many of these programs have adapted the original DPP structure and length, and have utilized CHWs or peer educators. These studies are typically less expensive and/or more feasible to administer in community-based settings and some studies have demonstrated health improvement similar to the original DPP. Our cultural adaptation of

DPP for South Asians also utilized and demonstrated high acceptability of the CHW model, *lending support to the concept of adapting DPP to be delivered by CHWs for this population.*

**B6. Incorporating CHWs into clinical teams can improve patient health outcomes.** The importance of CHWs in improving health outcomes for underserved communities has long been recognized by federal agencies and organizations, and by the Patient Protection and Affordable Care Act, in which CHWs have been identified as important members of the health care workforce. By acting as bridges between the community and health care system, CHWs have the potential to address health disparities and disseminate efficacious interventions to underserved communities. With the advent of the patient-centered medical home model, primary care practices increasingly aim to work in an integrated manner to coordinate care for a patient. There is a significant evidence base demonstrating the addition of CHWs to the primary care team can improve care for patients with chronic disease at low cost. There have been recent efforts to reimburse clinical settings for referral of pre-diabetic patients to YMCA-led DPP programs; *thus, the delivery of diabetes prevention by CHWs in clinical settings, coupled with reimbursement opportunities for this workforce, offers a unique opportunity for sustainable, scalable models for prevention.*

**B7. Electronic health records (EHRs) can improve primary and secondary prevention of diabetes.**

The US Preventive Services Taskforce (USPSTF) recommends screening adults in primary care settings with known risk factors T2DM, including high-risk racial and ethnic minority populations. Data available through EHRs can be used to identify candidates for needed follow-up, targeted risk-reducing interventions and can be designed to allow primary care physicians (PCPs) to easily refer patients to counseling and other services. The use of clinical decision support systems (CDSS) or alerts can increase provider adherence to screening and monitoring guidelines for diabetes management and prevention, such as foot and retinal exams, as well as cholesterol & hemoglobin A1c testing. EHRs can also assist providers in counseling patients through EHR-based goal-setting modules, intention exercises, and tailored reminders to encourage behavior change during clinical encounters with appropriate patients. There have also been recent efforts to utilize EHRs to identify and refer patients to community-based diabetes prevention programs, though none in small primary care settings that target high-risk immigrant communities. *The proposed project will build on this evidence-base by implementing EHR interventions to identify patients at-risk for T2DM using ADA adjusted BMI guidelines, and link them to CHW-led coaching to achieve weight loss.*

**B8. The effect of integrating EHR and CHW interventions has not been well-tested.** Despite the tremendous potential that both CHW and EHR-based interventions can have on improving health outcomes in minority communities, there have been few studies that have examined the impact of integrating the two interventions, and how best to engage both physician and non-physician members of the healthcare team, including CHWs, in effectively integrating EHR-based interventions into care planning. Studies are now beginning to demonstrate that EHR access and communication between the PCP and the CHW can facilitate the acceptance and effectiveness of emerging care management models and lead to improved patient outcomes, and no studies have been conducted in small primary care settings. *However, scalable and sustainable models that assess the cost, adoption, and maintenance process of integrating EHR and CHW intervention in clinical practice settings are needed.*

**Contributions**

The goal of this study is to test the effectiveness and assess the implementation process of an multi-level, integrated intervention to promote weight loss among South Asians at risk of T2DM, including two components: an EHR-based alert and registry function to increase identification of South Asian patients who are at-risk of diabetes, and CHW-led health coaching of registered patients with pre-diabetes to increase weight loss. This study is innovative in four main areas. *First*, the proposed intervention will foster the uptake and adoption of an evidence-based ADA recommendation for diabetes screening at lower BMI into clinical practice using HIT strategies (an alert and registry function) to enhance identification of pre-diabetes among South Asians, offering a scalable and replicable model to decrease disparities in a community with a high diabetes burden. Because the revised guidelines have not been systematically integrated into clinical practice, the implementation and testing of the proposed HIT

strategies represents an innovation of our project. Second, this is the first study to examine integration of a multi-level approach that combines EHR based tools to identify high risk patients, culturally adapted CHW-led coaching, and CHW-physician feedback to increase diabetes prevention in a high risk community. Though a limited number of studies have integrated EHR-CHW approaches and conducted referral to DPP programs, our study would represent the first to implement such a multi-level approach in small primary care practice settings in a high risk immigrant community. Our study uniquely assesses both effectiveness outcomes and implementation processes, thus informing the replication of integrated models in other primary care settings. Third, our culturally adapted DPP model has demonstrated efficacy, feasibility, and acceptability among South Asians at-risk for T2DM in community settings, and the proposed study offers a replicable model for clinical settings. Fourth, the project informs both the effectiveness and calculates costs of these interventions in team-based care approaches, thereby helping to develop potentially reimbursable and relevant sustainability strategies. Finally, given our partnership with a large payer organization and local health department, best practices for implementation of integrated EHR-CHW models at clinical sites will be generated that may be scalable to other insurer organizations and healthcare systems working with large immigrant populations facing a significant burden of chronic disease.

## C. Study Design

### C1. Overall Design/Site Selection/Site Enrollment

We will use a randomized controlled trial design with staggered-entry and a waitlist controlled group to compare the effectiveness of an alert and registry-driven CHW-led coaching compared with usual care among patients with BMI at baseline of  $\geq 23 \text{ kg/m}^2$ . Randomization will be at the individual-level and stratified by PCP, meaning eligible intervention and control participants will be randomized for each PCP. PCPs will be clustered into waves, aligning with the original stepped-wedge design. Entry into the study will be staggered in three waves, with each wave consisting of six to seven PCPs (See Figure 1). All 20 PCPs will be recruited and enrolled by month 6 of Year 2 (study period 6, Figure 1), and we will assign 6-7 practices into each of the 3 waves upon enrollment. For each PCP, there will be a total of two rounds of consecutive six-month CHW intervention periods: 1 month for recruitment and enrollment of intervention participants and five months of community health worker-led group education sessions (approximately one session per month). Data related to the study outcomes will be extracted from EHR systems a total three times (baseline, 6 month, and 12 month) for each PCP. Randomization at each PCP will occur during the first round. Prior to allocation into treatment group, each treatment participant will be matched to a control participant based on age, gender, and BMI. Intervention participants will be split into two groups and assigned to either first or second round. All control participants will be waitlisted during the first round and will be offered the full CHW group education sessions during the second round. PCPs will be placed into waves based on geographic location and CHW caseload considerations. PCPs will be eligible for participation if they have a) an overall patient volume of  $N \geq 1000$ ; b) at least 70% of the patient population is South Asian; and c) the practice has used EHR for at least 12 months. All PCPs will sign a Memorandum of Understanding (MOU) between the PCP and NYU outlining study commitments.

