**Figure 1. Recruitment, Enrollment, and CHW Intervention Timeline**

Participant Projections	Year 2			Year 3			Year 4			Year 5			Cumulative enrollment for entire study				
	Apr - June 2018	July - Sept 2018	Oct - Dec 2018	Jan - Mar 2019	Apr - June 2019	July - Sept 2019	Oct - Dec 2019	Jan - Mar 2020	Apr - June 2020	July - Sept 2020	Oct - Dec 2020	Jan - Mar 2021	Apr - June 2021	July - Sept 2021	Oct - Dec 2021	Jan - Mar 2022	Enrollment by wave
Wave 1																	
PCP1	Recruit/ Enroll N=48		CHW intervention	CHW intervention													
PCP2	Recruit/ Enroll N=48		CHW intervention	CHW intervention													
PCP3	PCP Recruitment	Recruit/ Enroll N=48	CHW intervention	CHW intervention													336 out of 960 target participants = 35%
PCP4	PCP Recruitment	Recruit/ Enroll N=48	CHW intervention	CHW intervention													
PCP5	PCP Recruitment	Recruit/ Enroll N=48	CHW intervention	CHW intervention													
PCP6	PCP Recruitment	Recruit/ Enroll N=48	CHW intervention	CHW intervention													
PCP7	PCP Recruitment	Recruit/ Enroll N=48	CHW intervention	CHW intervention													
Wave 2																	
PCP8	Recruit/ Enroll N=48		CHW intervention	CHW intervention													
PCP9	Recruit/ Enroll N=48		CHW intervention	CHW intervention													
PCP10	Recruit/ Enroll N=48		CHW intervention	CHW intervention													288 out of 960 target participants = 30%
PCP11	Recruit/ Enroll N=48		CHW intervention	CHW intervention													
PCP12	Recruit/ Enroll N=48		CHW intervention	CHW intervention													
PCP13	Recruit/ Enroll N=48		CHW intervention	CHW intervention													
Wave 3																	
PCP14	Recruit/ Enroll N=48		CHW intervention	CHW intervention													
PCP15	Recruit/ Enroll N=48		CHW intervention	CHW intervention													
PCP16	Recruit/ Enroll N=48		CHW intervention	CHW intervention													36 out of 960 target participants = 35%
PCP17	Recruit/ Enroll N=48		CHW intervention	CHW intervention													
PCP18	Recruit/ Enroll N=48		CHW intervention	CHW intervention													
PCP19	Recruit/ Enroll N=48		CHW intervention	CHW intervention													
PCP20	Recruit/ Enroll N=48		CHW intervention	CHW intervention													

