### **CHW Component:**

CHW Protocol. Patients that meet eligibility criteria will be drawn from registry lists and randomized to intervention or waitlisted control. Patients assigned to the intervention group will be sent an invitation letter to participate in the CHW intervention (See *Recruitment Letter for CHW Intervention*). Invitation letters will be followed up with phone calls by CHWs (See *Script for Telephone Screening for CHW Intervention*). In addition, a screening form (See *Telephone Screening Form for CHW Intervention*) will be completed to verify eligibility. CHWs will call patients a maximum of 10 times over a two-week period at varying times of day to invite them to enroll into the study. Patients assigned to the waitlisted control group will be recruited and contacted in the same manner as intervention participants except after completion of intervention rounds.

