#### *CHW Intervention*

Inclusion Criteria: Participants will be eligible for study participation if they meet the following criteria: a) self identify as South Asian; b) are at least 21 years of age and younger than age 75, c) had an appointment with a physician or mid-level clinician for routine non-emergent primary care in the last 12

Protocol: s17-00693

Version Date 9.28.21

months; d) have a BMI of  $\geq 23$ ; and e) have incident pre-diabetes as determined by HbA1c test (last A1c test date in the last 12 months).

Exclusion Criteria: Patients under the age of 21 and older than 75 will be excluded. Individuals with a diagnosis of diabetes or pre-diabetes during the 12 months prior to intervention implementation will be excluded. Pregnant women and all visits with an obstetrician gynecologist are excluded.

No children or vulnerable subjects will be enrolled in this study.

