### Power Calculation:

We conservatively estimate an 8% difference in effect size (i.e., >5% weight loss) comparing intervention and control group participants. Accrual of 1040 participants, evenly randomized to intervention or control groups, provide greater than 80% power to detect this difference, using a 2-sided, 0.05-level test (i.e., 52 participants (26 Intervention and 26 control participants per PCP). These calculations assume 15% loss to follow-up and enrollment of 20 PCP sites.

**Sampling:** Preliminary data from our practice needs assessment indicates that approximately 444 unique patients for every six months will have an office visit. Based on population estimates, we estimate that 29% of those individuals will be ineligible due to a pre-study period T2DM or pre-diabetes diagnosis (n=129) and approximately 69% of remaining patients will have a BMI  $\geq 23$  kg/m^2, making them eligible for the study (n=217). In our ongoing T2DM management CHW intervention among South Asians, screening to enrollment rate is 41%. For this study, we apply a conservative estimate that 30% of patients will consent to be contacted by a CHW and receive an HbA1c test (n=65). Based on populations estimate, we anticipate that 43% of those individuals will have pre-diabetes (n=28). Based on retention rates from our CHW studies, we conservatively estimate that approximately 85% of individuals assigned to a CHW will be followed up at six months (n=24). Thus, for each PCP, we will enroll approximately 24 patients every six months over a period of one year, resulting in total recruitment of 960 across 20 PCPs. This equates to an approximate CHW caseload of 13 patients per month for a part-time CHW, consistent with caseloads from our previous studies.

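### Intervention patients face a telephone eligibility check after randomisation (about six months after it in round 2) that controls do not face before their outcomes are used, with no reference date and no rule for those who fail it

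*Combined protocol and SAP*

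**What the plan says.** Section I.C1 sets the calendar. Each practice has "two rounds of consecutive six-month CHW intervention periods: 1 month for recruitment and enrollment of intervention participants", each followed by five months of group sessions. It states that "Randomization at each PCP will occur during the first round" and that "Intervention participants will be split into two groups and assigned to either first or second round".

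Section I.C2 (CHW Component), repeated in section VI.A, sets the order of events: "Patients that meet eligibility criteria will be drawn from registry lists and randomized to intervention or waitlisted control". Intervention patients then receive a letter and calls from a community health worker, and a screening form "will be completed to verify eligibility". Controls are approached only after the intervention rounds. Their outcomes come from the EHR alone, under a requested waiver (section I.C2 on waitlisted controls; section VI.G, Control Participants).

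Section II requires, among other things, a primary care visit within 12 months, BMI of at least 23, and that patients "have incident pre-diabetes as determined by HbA1c test (last A1c test date in the last 12 months"). No date is given from which the inclusion windows are counted. The separate exclusion for a prior diagnosis is counted back from intervention implementation, which is not defined as round 1, round 2 or practice go-live.

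Section III.B1 makes weight loss of at least 5% at six months the primary outcome and HbA1c reduction a secondary one. It mentions intent-to-treat only in a remark on multiple imputation.

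"Figure 1. Recruitment, Enrollment, and CHW Intervention Timeline" shows, for each practice, a single Recruit/Enroll block of 48 ahead of both coaching blocks.

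**The concern.** Eligibility should be settled before allocation, or at least judged in the same way in both arms. Here one arm gets a second look after allocation and the other does not, at least before its outcome data are used. The delay matters because the criteria do not stand still. A visit or HbA1c date that was inside 12 months at randomisation can fall outside it by the round-2 call, and HbA1c and weight can change while the patient waits. Both are trial outcomes, so a check on current values would select intervention patients on what happened to them after randomisation, while comparable controls stay in.

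No section says what becomes of a randomised patient who fails the telephone check. Section VI.G covers EHR collection for intervention patients through their informed consent, and the EHR-outcome waiver is requested for controls. A screened-out intervention patient therefore has no stated route into the analysis. If such patients are dropped, the randomised comparison is lost for part of one arm. If they are kept, they are uncoached and the estimated effect is diluted. The plan should say which applies.

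**Working it through.** **1. The plan's own figure.** The power paragraph in section III.B1 gives 1040 patients allocated evenly, 15% loss, an 8-point difference, two-sided 0.05 and more than 80% power. Analysed per arm: 520 × 0.85 = 442. The control rate p1 is not stated, so I varied it, with p2 = p1 + 0.08, q = 1 − p, p̄ the mean of p1 and p2, and

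power = Φ{[0.08√442 − 1.96√(2p̄q̄)] / √(p1q1 + p2q2)}.

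| Assumed control rate | Power |
|---|---|
| 5% | 0.987 |
| 10% | 0.930 |
| 15% | 0.859 |
| 20% | 0.796 |

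The claim holds for control rates up to about 19.7%.

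**2. When the check happens.** Round 1 is month 1 for recruitment and months 2 to 6 for sessions, so round 2 recruits in month 7. With one randomisation in round 1, ahead of the invitation letters, the lag from allocation to the call is up to about one month in round 1 and about six months in round 2.

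**3. Lapsed windows, if the 12 months are counted back from the call.** A test aged D months at randomisation is out of window after a lag of L months when D + L > 12. If D is uniform over 0 to 12 and there is no retest (both assumptions), the lapsed share is L/12:

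- round 1: 1/12 = 8%
- round 2: 6/12 = 50%
- round 2, if every test was under six months old at randomisation: 0%

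The documents give no distribution of test dates, so 0% to 50% of round 2 is a range and not an estimate.

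**4. Overlap with outcomes.** A retested patient whose HbA1c leaves 5.7–6.4% no longer meets the pre-diabetes criterion. For BMI, if it is judged at the call: 23 / 0.95 = 24.2, so a patient starting at 23.0 to 24.2 who achieves the primary outcome ends below 23. This shows that a responder could become ineligible. It does not count how many would.

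**5. What removal would do to the estimate.** Assume an equal split (520 / 2 = 260 per round; not stated, though the sampling text says "we will enroll approximately 24 patients every six months over a period of one year"), no true effect, a 10% response rate in both arms, and 20% of round 2 (52 patients) screened out and not analysed, with response rate r.

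Remaining round-2 rate = (0.10 − 0.20r) / 0.80; arm rate = (260 × 0.10 + 208 × round-2 rate) / 468.

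| r | Remaining round-2 rate | Arm rate | Shift in points |
|---|---|---|---|
| 0% | 12.5% | 11.1% | +1.1 |
| 30% | 5.0% | 7.8% | −2.2 |
| 50% | 0% | 5.6% | −4.4 |

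The planned effect is 8 points. The sign depends on who is removed: losing non-responders flatters the intervention, and losing responders penalises it.

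**6. Loss of numbers alone.** If 10% to 50% of the 260 leave the analysis with no selection, power is 0.985–0.972, 0.924–0.891 and 0.851–0.806 at control rates of 5%, 10% and 15%. It stays above 80% throughout, so the issue is selection rather than precision.

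**The case against.** The strongest reply is that eligibility is already settled from the registry before allocation, and that no section says visit dates, HbA1c or BMI are tested again at the call. Section I.C1 describes the population by BMI at baseline, which argues against judging BMI six months later. The screening form is not among the documents, and a telephone call cannot measure weight or HbA1c; it might check only ethnicity, age, pregnancy or a reported diagnosis. HbA1c tests may also be recent, because the alert prompts new ones (section I.C2) and the sampling funnel includes a test at recruitment (section III.B1). Finally, section III.B1 refers to intent-to-treat, and section III.A2 collects EHR data from both arms.

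Much of this stands. It makes re-application of the criteria an inference, weakens the BMI part, and pulls the likely number towards the low end. It does not close the gap. The form's stated purpose is to verify eligibility, the inclusion windows have no anchor, the intent-to-treat remark concerns imputation, and the EHR-outcome waiver names controls.

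A reader might infer that half of the intervention arm is certain to be culled, that round 2 alone is affected, or that improvers are removed so the trial is biased against the intervention. The documents support none of these. The split is not stated to be equal, and the criteria actually re-tested are unknown. Round-1 patients are also checked after allocation, with a short lag. A check on current HbA1c would remove patients who progressed as well as those who normalised.

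**Conclusion.** The concern holds as a gap in design and wording. The text places an eligibility check after randomisation for intervention patients, about six months after it for round 2, with no equivalent for controls before their outcomes are used. The criteria in section II can drift over that interval, and one of them (two, if BMI is not read as baseline) overlaps the outcomes. Nothing ensures that a patient who fails the check is analysed.

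The number affected cannot be derived from the documents. Near 0% to about half of round 2 is the range for lapsed HbA1c windows, and the upper end needs uniform test dates and no retesting. The shifts of +1.1 to −4.4 points are illustrations that assume 20% removal, an equal split, a 10% response rate and exclusion from the analysis; they establish neither a size nor a direction. The change is worth making because it is cheap and removes a source of bias. Confidence is medium, because the content of the screening form is not shown.

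**What to change.** - **Sections I.C1 and II:** state that eligibility is determined once from the EHR as at the randomisation date, identically for controls and both rounds, with every 12-month window counted back from that date.
- **Sections I.C2 (CHW Protocol) and VI.A:** state that the call does not re-apply the visit, HbA1c or BMI criteria as study eligibility.
- **Section III.B1:** state that every randomised patient is analysed in the assigned arm whatever the result of the telephone screen.
- **Section VI.G:** extend the EHR waiver request to intervention patients who are screened out or not enrolled, so that their outcomes can be used.
- **Figure 1:** reconcile its single recruitment block with the recruitment month per round in section I.C1.

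Figure 1 might suggest screening everyone in the first month instead. That is not a good substitute. Consent goes with the screening call, and the baseline survey follows within two weeks of consent (section I.C2), so round-2 patients would be consented and surveyed about six months before coaching.

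The cost is protocol wording and an amended waiver request, with no extra patients or procedures. The downside is that some patients analysed in the intervention arm will not have been coached, which dilutes the estimated effect.
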